13.4 Detailed Description of the Efficacy Analysis

Though p-values and CIs will be displayed as described below, it is of note that the study is not powered to demonstrate statistical significance. These are only displayed as a preliminary investigational tool to aid with planning future studies. All efficacy endpoint values will be included in listings.

13.4.1 Eyelid Discomfort

Baseline to All Follow-up Eyelid Scrubs for Study Eye:

Within each treatment group, Eyelid Discomfort at the [REDACTED] baseline and follow-up visits ([REDACTED] [REDACTED] will be tabulated using continuous summary statistics (n, median, standard deviation, median, minimum and maximum); one-sample Student's t-distribution CIs and p-values will be used for comparing change from baseline to follow-up visits. Between treatment groups, two-sample Student's t-distribution CIs and p-values are calculated to compare the Eyelid Discomfort scores at each visit as well as the change from baseline.

[figure not shown]
RUN;

13.4.4 Composite Score of Eyelid Margin Redness, Eyelid Debris, and Eyelid Discomfort

The composite score of Eyelid Margin Redness, Eyelid Debris, and Eyelid Discomfort is defined as the sum across the three measurements at a particular visit. If any of the assessments is missing, the composite score will be set to missing.

The composite endpoint based on changes from baseline

15 Safety Analyses

All safety analyses will be conducted using the Safety population.

15.1 Adverse Events

An AE is defined as any untoward medical occurrence in a subject or clinical investigation subject administered a pharmaceutical product and which does not necessarily have to have a causal relationship with this treatment.

An AE can therefore be any unfavorable and unintended sign (including an abnormal laboratory finding), symptom, or disease temporally associated with the use of a medicinal (investigational) product, whether or not considered related to the medicinal (investigational) product. Lack of efficacy will be reported as a treatment failure, not as an AE.

Treatment-emergent adverse events (TEAE) are defined as any event that occurs or worsens on or after the day that randomized study treatment is initiated. Adverse events recorded in the eCRF which began prior to treatment will not be included in the summary tables but will be included in the AE data listings.

The severity of an AE should be categorized as mild, moderate, or severe per Investigator's judgment with the following scale in consideration:

- **Mild:** Awareness of a sign or symptom that does not interfere with the subject's usual activities or is transient, resolved without treatment and with no sequelae
- **Moderate:** Interferes with the subject's usual activities, and/or requires symptomatic treatment
- **Severe:** Symptom(s) causing severe discomfort and significant impact of the subject's usual activities and requires treatment

Adverse events missing severity will be counted as severe.

A determination of the relationship between an AE and the study medication must be made by the Investigator for each AE. The following terms to evaluate the causality of the AE with the study drug should be used:

- **Unrelated:** A simultaneous disease, a simultaneous treatment or any other known cause is clearly responsible for the safety event and the AE is not related to the study medication.
- **Unlikely:** On the basis of the available knowledge regarding the subject's history, the disease process, the timing of the safety event in relation to the application of the study medication and the mode of action of study medication, a relation between the study medication and the safety event is unlikely, but cannot be totally excluded.
- **Possible:** This relation exists when the safety event follows the reasonable chronological sequence from the moment of the study medication application, but when the safety event could also have been caused by the clinical condition of the subject or by other treatment administered to the subject.
- **Probable:** This relation exists when the safety event follows a reasonable chronological sequence from the moment of the study medication application, corresponds to a known effect of the study medication, is confirmed by the observation of an improvement upon discontinuation of the study medication application, and therefore the study medication is the most probable of all the causes.
- **Definite:** This relation exists when the safety event follows a reasonable chronological sequence from the moment of the study medication application, corresponds to a known effect of the category of the studied medication, is confirmed by the observation of an improvement upon discontinuation of the study medication, and no other reasonable cause exists.

Treatment-emergent adverse events possibly, probably, or definitely related to study drug will be considered treatment-related TEAEs. Any TEAEs with a missing relationship will be considered treatment-related TEAEs.

An SAE is any untoward medical occurrence that at any dose:

- Results in death;
- Results in-subject hospitalization or prolongation of existing hospitalization;
- Results in persistent or significant disability/incapacity;
- Results in a congenital anomaly/birth defect;
- Results in life-threatening illness or injury (Note: The term "life-threatening" in the definition of "serious" refers to an event in which the subject was at risk of death at the time of the event; it does not refer to an event which hypothetically might have caused death if it was more severe, or had continued untreated); or
- Results in a significant and persistent loss or impairment of vision.

Additionally, medical events that may not meet these criteria may be considered an SAE if, based on the medical judgment of the Investigator, such medical events may require an intervention to prevent any of the outcomes listed above.

An overall summary will be presented that includes the number of events and the number and percentage of subjects who experienced at least one AE and TEAE, by treatment group and over all subjects. This summary will also include breakdowns of TEAEs further categorized as treatment-related TEAEs, serious AEs (SAE), TEAEs leading to early treatment discontinuation, TEAEs leading to death, and TEAEs by maximum severity.

Additional summaries of TEAEs will be provided showing the number of events and the number and percentage of subjects who experienced at least one TEAE by treatment group and over all subjects. Ocular and Non-ocular TEAEs will be summarized together using discrete summary statistics and presented by treatment group at the subject and event level by SOC and PT. If a subject reports the same PT multiple times within the same SOC, that PT will only be reported once within that SOC. As with the PT, if a subject reports multiple conditions within the same SOC, that SOC will only be reported once. In the summary, SOCs will be listed in ascending alphabetical order; PTs will be listed in order of descending frequency for all subjects within each SOC.

Separate summaries will be provided for the following categories of AEs:

- Treatment-Related TEAEs
- TEAEs by Relationship to Study Drug
- TEAEs by Maximal Severity

The number of subjects with any TEAEs (along with percentages) will be tabulated by SOC and PT within each SOC by treatment group. To count the number of subjects with any TEAEs, if a subject has multiple TEAEs coded to the same PT within the same SOC, the subject will be counted once under the maximum severity.

All TEAEs will be presented in a subject listing. The TEAEs leading to study treatment discontinuation will be listed separately. In addition, all SAEs will be presented in a separate listing.

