10.5 Adverse Event Reporting

In this study, subjects should be encouraged to report AEs spontaneously or in response to general, non-directed questioning (e.g., "How has your health been since the last visit?"). If it is determined that an AE has occurred, the Investigator should obtain all the information required to complete the AE Form(s).

Additionally, subjects will be instructed to contact the Investigator, and/or study coordinator if any significant AEs occur between study visits.

From the signing of the ICF on the day of the Screening Visit, all AEs must be recorded on the appropriate AE form. All AEs must be reported whether or not considered causally related to study medication. For every AE, the Principal Investigator will provide an assessment of the severity and causal relationship to study medication, document all actions taken with regard to study medication, and any other treatment measures for the AE.

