11.5.3 Safety Analysis

Subject disposition, demographics, and baseline characteristics will be summarized and presented in data listings.

Safety analyses are based on the safety dataset. The safety dataset will include all subjects who receive at least one dose of study medication.

Adverse events (AEs) will be coded using the MedDRA dictionary. The safety analysis will summarize treatment emergent ocular and systemic AEs for all treated subjects, using discrete summaries at the subject and event level by system organ class and preferred term for each treatment group.

A treatment-emergent AE (TEAE) is defined as an AE that occurred on or after the treatment was initiated. Ocular TEAEs by treatment group: NCX 4251 0.1% and placebo QD and BID, will be summarized, by relationship to study drug, and by severity. Non-ocular TEAEs will be summarized by treatment group as follows: non-ocular TEAEs, by relationship to study, and by severity. Serious AEs (SAEs), AEs resulting in study drug discontinuation, and deaths will be presented in data listings.

Other ocular safety data including visual acuity, slit-lamp biomicroscopy, IOP, and dilated ophthalmoscopy will be summarized by treatment group and visit using descriptive statistics.

Changes or shifts from baseline will also be summarized where appropriate. For assessments performed by eye, study eye and fellow eye will be summarized separately.

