This SAP is being written with due consideration of the recommendations outlined in the most recent International Conference on Harmonisation (ICH) E9 Guideline, titled Guidance for Industry: Statistical Principles for Clinical Trials, and the most recent ICH E3 Guideline, titled Guidance for Industry: Structure and Content of Clinical Study Reports.

This SAP describes the data that will be analyzed and the subject characteristics, efficacy, and safety assessments that will be evaluated. This SAP provides details of the specific statistical methods that will be used. The statistical analysis methods presented in this document will supersede the statistical analysis methods described in the clinical protocol. If additional analyses are required to supplement the planned analyses described in this SAP, they may be completed and will be identified in the clinical study report.

2 Study Objectives

Primary Objective

The primary objective of this clinical study is to select the dose(s) of NCX 4251 to be advanced into the next stage of development.

Secondary Objectives

The secondary objectives of the study are to assess the safety and tolerability of the study medication applied once daily (QD) and twice daily (BID).

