8.2 Missing or Inconclusive Data Handling

Efficacy analyses will be primarily based on the ITT population with observed data only. To check for robustness of outcomes, missing data will be imputed using last time consistent (pre- and post-eyelid scrub) observation carried forward for the composite endpoint analysis by eye.

AEs with completely missing onset dates will be considered treatment-emergent. AEs with a missing month and day of onset will be considered treatment-emergent unless the onset year is prior to the year of first dose of study treatment. AEs with a missing day of onset will be considered treatment-emergent unless (1) the onset year is prior to the first dose of study treatment or (2) the onset year is the same as the year of first dose of study treatment and the onset month is prior to the month of first dose of study treatment. AEs

missing a relationship will be considered treatment-related. Medications with missing start dates will be considered concomitant medications unless (1) the medication start year is prior to the year of the first dose of study treatment or (2) the medication start year is the same as the year of first dose of study treatment and the medication start month is prior to the month of first dose of study treatment, in which case these will be considered prior (and possibly concomitant depending on the end date) medications. Medications with missing end dates will be considered concomitant medications unless (1) the medication end year is prior to the year of first dose of study treatment or (2) the medication end year is the same as the year of first dose of study treatment and the medication end month is prior to the month of first dose of study treatment, in which case these will be considered prior medications. In the event that a medication end date is prior to the medication start date, the medication end date will be considered as one day after the medication start date for the purposes of determining whether this is a prior and/or concomitant medication. The actual reported AE onset dates and medication start and end dates, including any unknown portions, will be included in the appropriate listings as entered by site personnel.

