15.4 Slit Lamp Biomicroscopy Examination

The slit lamp examination will be performed prior to any contact assessments and instillation of any drops at each specified visit.

[REDACTED]
[REDACTED] The following structures will be examined at each visit: eyelid (other than eyelid margin redness and eyelid debris), conjunctiva [REDACTED] cornea, lens, iris, pupil, and anterior chamber.

A subject listing of the slit lamp biomicroscopy parameters will also be produced.

17 Changes from Protocol Stated Analyses

The protocol describes analyses pooling just the placebo arms from Cohorts 1 and 2; however, the SAP includes analyses pooling both the placebo arms from each cohort and the NCX 4251 arms from each cohort.

The protocol describes AE summaries separately for ocular and non-ocular AEs. Given the low number of expected AEs overall, the SAP combines summaries of ocular and non-ocular AEs. The separation of AEs by SOC will clearly identify which AEs are ocular and which are not.

18 References

There are no references for this SAP.

19 Revision History

The following revisions were made to version 1.0 of the SAP, after approval of version 5.0 of the study protocol.

Section	Revision	Rationale
All	Administrative changes	To provide consistency and better readability
1	Revised to version 5.0 of the protocol	Protocol amendment
2.2 – 2.4	Revised and reordered endpoints	Protocol amendment
3.1, 4, 7.2, 8, 13.2	Updated details to match the current protocol and analysis strategy	Protocol amendment
3.2 and Appendix A	Moved the schedule of assessments to the appendix	To provide better readability in the SAP text
6.1 and 6.2	Separated Section 6 into two sections 6.1 and new section 6.2; added Section 6.2 to discuss output data formats	To detail the formats of SDTM, ADaM, and associated deliverables
13.4	Added details of the analyses including both eyes and the Clopper Pearson CI calculations	To fully describe the statistical analyses for efficacy endpoints, including the statistical modeling and specific endpoints to which the analyses apply
14.2.2	Add description of the meibomian gland assessments used for Cohort and how the data will be analyzed	Protocol amendment
15.1	Added more detail about AE summaries	To provide a better explanation of the AE summaries included in the study
19	Added revision history	To document the changes from version 1.0 to version 2.0 of the SAP

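### SAP 15.1 counts as treatment-emergent an event that worsens on treatment or starts on the first treatment day, but its next sentence bars from the summary tables any AE that began before treatment

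*SAP*

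**What the plan says.** The SAP and protocol contain these rules on which AEs are tabulated.

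- SAP 15.1 defines a TEAE as "any event that occurs or worsens on or after the day that randomized study treatment is initiated".
- The next sentence of SAP 15.1 states: "Adverse events recorded in the eCRF which began prior to treatment will not be included in the summary tables". Those events go to the AE listings instead.
- Protocol 11.5.3, repeated in the synopsis, is narrower: "A treatment-emergent AE (TEAE) is defined as an AE that occurred on or after the treatment was initiated". It does not mention worsening.
- SAP 1 gives the SAP priority: "The statistical analysis methods presented in this document will supersede the statistical analysis methods described in the clinical protocol".
- The SAP section headed "17 Changes from Protocol Stated Analyses" records two differences, one on pooling of arms and one on combining ocular and non-ocular AE summaries. The change to the TEAE definition is not among them.
- Protocol 10.5 starts AE collection before dosing: "From the signing of the ICF on the day of the Screening Visit, all AEs must be recorded on the appropriate AE form". Protocol 7.2 puts Baseline/Day 1 three to seven days after Screening.
- The SAP 15.1 overall summary reports "the number and percentage of subjects who experienced at least one AE and TEAE, by treatment group and over all subjects".

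**The concern.** A definition and the table rule that follows it should select the same events. Here the definition has two routes, new onset and worsening, and it runs from the calendar day of first treatment. The exclusion has one route, onset, and it runs from treatment itself. A programmer who codes the exclusion as written would drop events that the SAP has just called treatment-emergent. One who codes the definition would keep them.

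Safety and tolerability are the secondary objectives, and TEAE incidence is a safety endpoint in SAP 2.3. What is at stake is whether the TEAE tables (14.3.1 to 14.3.5 in SAP 20) report the quantity that the SAP defines.

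**Working it through.** The plan gives no figure to reproduce, so the check applies both SAP 15.1 sentences to each possible timing of an AE.

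| Timing of the AE | TEAE by the definition? | Allowed in the tables by the next sentence? | Agree? |
|---|---|---|---|
| Starts after the first application | Yes | Yes | Yes |
| Starts before Day 1, does not worsen | No | No | Yes |
| (a) Starts after consent and before first dose, worsens on treatment, keeps its original onset date | Yes | No | **No** |
| (b) Starts on Day 1 before the first application | Yes | No | **No** |

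**Can (a) occur?** AEs are recorded from consent, and first dosing follows 3 to 7 days later, so a pre-dose AE record can exist. The conflict arises only if the worsening stays on that record. If it is entered as a new AE with a later onset, both sentences admit it. The documents shown do not say which practice applies.

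**Can (b) occur?** In the Protocol 7.2 order for Baseline/Day 1, slit lamp examination, IOP measurement and supervised eyelid scrubs all come before randomization and the first application. An AE can therefore start on the treatment day but before treatment.

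**What is not affected.**

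- A condition held as medical history and first recorded as an AE when it worsens on treatment is not an AE recorded as having begun before treatment.
- Lack of efficacy is handled as treatment failure (Protocol 10.1, SAP 15.1), and so is early exit for worsening of the disease (Protocol 10.3). Neither is an AE.

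**Effect of one affected subject with no other TEAE.** Change in subject-level incidence = 1/n, with planned sizes from Protocol 3.1:

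- arm of 10 (NCX 4251 QD, NCX 4251 BID or placebo BID): 1/10 = 10 percentage points;
- placebo QD, 5 subjects: 1/5 = 20 percentage points;
- all-subjects column, 15 + 20 = 35: 1/35 = 2.9 percentage points.

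These figures show how coarse the tables are. They do not estimate how often the problem will occur.

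**The case against.** The strongest reply is that the definition plainly governs and that the second sentence is meant only to set aside AEs that are not treatment-emergent. That is probably the intent. The word worsens also has real work to do for medical-history conditions first reported as AEs on treatment, so the two sentences coexist for most events. Both points stand and they narrow the reach. They do not remove the conflict, because the exclusion depends on when the AE began and not on whether it is treatment-emergent.

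A second reply is that recording conventions belong in separate documents, namely the Data Validation Manual (SAP 6.1) or the Data Management Plan (Protocol 13.5). A convention of opening a new record at worsening would dispose of case (a). That is possible and cannot be checked from these documents. It would not resolve case (b).

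A third reply is that, read literally, the tables simply follow the protocol's onset-only definition. That is broadly true for case (a). But the SAP says that its own methods take precedence, and it does not declare the change.

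Some stronger readings are tempting and are not supported:

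- A reader might infer that safety data are lost. They are not: SAP 15.1 keeps these events in the listings, and SAP 21 lists all adverse events.
- A reader might work out effects for pooled active or pooled placebo columns. SAP 15.1 states AE columns by treatment group and over all subjects only, so pooled AE columns are not established.
- A reader might attach a probability to at least one such event. The documents give no rate, so the result would only restate an assumption.
- A reader might treat the partial-date rule in SAP 8.2 as a second substantial fault, since it too uses onset alone ("onset month is prior to the month of first dose of study treatment"). It matters only when the onset day is unknown and a month end falls between onset and first dose. Otherwise that rule defaults to treatment-emergent.

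**Conclusion.** Wrong as written; severity minor. The two adjacent sentences in SAP 15.1 give opposite answers for cases (a) and (b), and nothing in the text shown reconciles them. Confidence is high for the wording. Any effect on the counts is unknown and probably very small, given a window of 3 to 7 days plus the pre-dose part of Day 1 in about 35 subjects. Case (a) further depends on the worsening being kept on the original record and being identifiable there. If an affected subject has no other TEAE, that one subject shifts incidence by 10 points in an arm of 10 and by 20 points in placebo QD. This is a question of table accuracy in an early-phase study without formal hypotheses. The undeclared addition of worsening to the protocol's definition holds whether or not any such event occurs.

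**What to change.** 1. In SAP 15.1, replace the exclusion sentence with: *AEs that are not treatment-emergent under the definition above are not included in the TEAE summary tables but are included in the AE listings.* This resolves (a) and (b) together. Adding only an exception for worsening would leave (b) in conflict.
2. Use one anchor in both sentences, either the day or the time of first application. If time is chosen, confirm that onset time is available for Day 1 events; the documents shown do not say.
3. State how a worsening is identified: from a new AE record dated at the worsening, or from a documented review of existing records. SAP 1 and 8.4 tie the final analysis to the unmasking of Cohort 2. A review should therefore be masked for Cohort 2, and for Cohort 1 the SAP should state whether it was masked.
4. In SAP 17, list that the SAP adds worsening to the protocol's onset-only TEAE definition.

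The cost is a few sentences in SAP 15.1 and 17. If worsening was not captured as a new record, add a short documented review of AE records with onset before first dose. No new data collection or change to study procedures is needed, unless time is chosen as the anchor and onset times were not recorded.
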